### 7.3.2 Secondary outcomes

1. Examine models to predict non-daily adherence based on TFV/FTC and FTC-TP/TFV-DP in DBS.

We assume the modeling approaches of Aim-1. We will first consider a saturated model allowing a separate mean for each dose/adherence group. The results will then be compared to a reduced model with a class variable indicating non-daily dosing groups" or 100% dosing (that is, the effect of "non-daily dosing" adherence does not differ by dose groups). Drug concentration predictors of "non-daily dosing" will focus on TFV-DP in relationship to other drug moieties such as FTC-TP and FTC and TFV. For instance, the ratio of TFV-DP to FTC-TP may be used as a predictor of "2" versus "4" dosing per week. A proportional odds logistic approach which allows for an ordinal outcome and extensions which control for correlations between repeated measurements on a subject will be utilized in SAS or R statistical software. In addition, we will employ PK models (see Aim-1) to simulate TFV-DP to FTC-TP ratios for other dose regimens and estimate cut points for predicting non-daily dosing patterns.

2. Examine relationships among drug concentrations in plasma, RBC, DBS, and PBMC.

We will use mixed and non-linear mixed effects models to determine if concentrations in various matrices are related.

3. Evaluate the influence of demographics, biological on drug concentrations.

Kruskal-Wallis parametric test will be used to compare demographics and key study variables (e.g., age, pregnancy, HCT, contraception use, study arm, BMI, eGFR). Non-linear mixed effects models also will be used to probe covariate effects on PK. Secondary analyses are considered hypothesis generating and will not correct for multiple comparisons.

4. Compare drug concentrations in DBS from fingerstick versus transferring blood from blood tubes.

Since these are paired DBS samples, we will compute the ratio of TFV-DP in the two samples and a mixed model on the natural log of the ratio will be utilized to determine if CI is within 0.8 and 1.25, indicating equivalence. Bland-Altman analyses will also be evaluated.

#### 7.4 Sample Size Considerations

The overall sample size was chosen to have up to 18 cisgender women in each relevant group (overall, n=54 non-pregnant cisgender women) sufficient to provide precise information on drug concentrations and to balance feasibility, efficiency, and provide robust TAF/FTC data in DBS for cisgender women. The sample size for drug concentration parameters is based on ensuring precision in the estimates to accurately describe the concentration kinetics of TAF/FTC in non-pregnant cisgender women and is consistent with multiple DOT PrEP studies done in US populations. The precision desired is a mean TFV-DP in DBS at steady state within  $\pm 15\%$  of the true population mean. The mean ( $\pm$  standard deviation) TFV-DP at steady-state in HIV-uninfected US cisgender men and cisgender women following directly observed doses of 25 mg TAF/200mg FTC once daily for 12 weeks was  $2381 \pm 601$  fmol/punches [coefficient of variation (CV) of 25%] (*Anderson et al*). Based on this variability and assuming average TFV-DP results are normally distributed, to be 90% confident that the DBS TFV-DP sample mean is within 15% of the true mean, a sample size of 15 participants is required for non-pregnant cisgender women with conservative assumptions. With the planned enrollment of 18 cisgender women per group for this study, even a 10% non-completion rate at 8 weeks of DOT therapy, we provide ample data to estimate steady-state means to within 10% in cisgender women.

#### 7.5 Randomization and Blinding Procedures

The study design will be an open-label, randomized study with three arms. The randomization assignment will be made at enrollment if the participant is eligible and agrees to enroll. Randomization will be according to the PrEP dosing frequency and vaginal tissue collection plan (either sampling day 4 or day 7) 1:1:1 fashion programmed by the study statistician and generated from REDcap.

The allocation of participants for the 3 study arms will be the following:

	2 doses per week	4 doses per week	7 doses per week	Total
Total	18	18	18	54

### 8 HUMAN SUBJECTS CONSIDERATIONS

#### 8.1 Ethical Review

The protocol, site-specific informed consent form, participant education and recruitment materials, and other requested documents — and any subsequent modifications — will be reviewed and approved by the University of Washington Human Subjects Ethical Committee and the Scientific and Ethics Review (SERU) Committee of the Kenya Medical Research Institute responsible for oversight of research conducted at the study site.

Subsequent to initial review and approval, the responsible IRBs/ECs will review the protocol at least annually. The Investigator will make safety and progress reports to the IRBs/ECs at least annually, and within three months of study termination or completion. These reports will include the total number of participants enrolled in the study, the number of participants who completed the study, all changes in the research activity, and all unanticipated problems involving risks to human subjects or others.

## **8.2 Informed Consent**

In obtaining and documenting informed consent, the investigators will comply with all applicable local and/or domestic regulatory requirements and will adhere to Good Clinical Practices and to all ethical principles from the Declaration of Helsinki. A trained research staff person will conduct the informed consent process. Written informed consent will be obtained individually from each participant. Staff will explain the study, read the consent form, and answer any questions the participant may have. Consent information will describe the purpose of the study, the procedures to be followed, and the risks and benefits of participation, in accordance with all applicable regulations. We will translate the forms into the local language (Kiswahili) and verify the accuracy of the translation by performing an independent back-translation. The consent process will occur either in English or the local language (Kiswahili) depending on the participant's preference. We will perform paper-based and/or electronic-based consenting of participants. For the electronic version, we will program the complete consent form with signature pages onto tablets and participants will read along on the tablet during the consenting process. The study team member conducting consent will allow the participant time to ask any questions that they may have before signing the consent form. After we have ensured that participants have read and understood the consent forms, we will ask them to append their signature on the tablet. The signature will be stored electronically. In addition, any participant who wants their consent form to take home will have a paper copy printed and given to them. At each visit after enrollment, participants will have the opportunity to ask questions and the study staff will remind them their participation is voluntary. Participants will be informed that they may withdraw from any of the research procedures at any time, without it affecting the care they receive at the clinic.

## **8.3 Voluntary Participation**

The consenting process will emphasize and give information that study participation is voluntary and that the participant can withdraw from the study at any time without losing the care they would otherwise receive.

## **8.4 Potential Risks to Human Subjects**

Safety assessment will be measured in all participants: serious adverse events (SAEs), related Grade 3 and 4 AEs and discontinuations, and side effects. The medical risks of blood collection and vaginal tissue collection are small, with some anticipated mild discomfort from vaginal speculum insertion, and venipuncture. Participants may become embarrassed, worried, or anxious while undergoing pelvic exams for collection of samples.

### **Risks related to non-daily TAF-FTC PrEP dosing**

Descovy® is approved by the U.S. Food and Drug Administration for PrEP use in cisgender men and transgender women. However, Descovy® is not yet indicated in at risk cisgender women because the effectiveness in cisgender women has not been evaluated. Only daily FTC/TDF PrEP is currently approved for PrEP in cisgender women but large studies of Descovy® (F/TAF) PrEP for cisgender women are currently planned or ongoing in African cisgender women. We have carefully considered the risk for TAF-FTC PrEP and non-daily dosing (i.e., 2 or 4 doses per week) in cisgender women, including the potential for risk of HIV infection. The non-daily dosing is needed to help investigate and demonstrate dose proportionality of TVF and TVF-DP concentrations. For people living with HIV, Descovy® has been approved by the FDA for treatment of HIV in combination with other antiretroviral drugs since 2016, with very favorable safety profile compared to FTC/TDF. As detailed in the eligibility section, to minimize risks

only cisgender women at low risk of HIV based on the Kenya guidelines for PrEP will be enrolled and cisgender women will receive a full package of HIV prevention, including risk reduction counseling, condoms and STI treatment at each visit. We will also perform monthly HIV testing. We will use Kenya national PrEP guidelines to guide identification of cisgender women at elevated risk of HIV to guide recruitment into this study. Cisgender women found to be at risk for HIV through the screening process will be given PrEP at the clinic if interested or referred at their clinic of choice. Each visit will include risk-reduction counseling for all cisgender women. All participants in this study will have HIV test at baseline and then every 4 weeks and study drug will be immediately discontinued in case of seroconversion.

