#### **4.7 Toxicity Management**

Safety related laboratory testing will be performed at study entry and at week 8 and or as indicated by clinician during follow up. If enrollment occurs more 30 days after screening, entry safety labs will be repeated. These include HIV rapid testing, complete blood count, HBV surface antigen, serum creatinine, and urine pregnancy test. Toxicity will be managed in consultation with a clinician on the protocol. The clinician may discontinue the study drug at any time if he/she feels that continued use would be harmful to the participant. The PSRT should be consulted when possible. The PSRT will be consulted when considering further holding or recommencing study medication.

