#### **4.8 HIV Seroconversion**

Frequent testing for HIV acquisition during the study period will allow prompt cessation of study drug in an HIV-infected participant, minimizing the risk that resistant virus will emerge. Therefore, HIV testing will be performed at all monthly study visits. HIV rapid testing and specimen collection will be completed prior to administration of study medication. Participants who have any reactive or positive HIV test result after initiating PrEP will be instructed to discontinue study drug immediately and will have further testing to clarify their HIV infection status, as described in Section 5.3. Any enrolled participant who is confirmed to have acquired HIV infection during the study will permanently discontinue study product and will be transitioned to a local HIV care clinic for appropriate follow-up and clinical management. Procedures for participants who acquire HIV infection are described in Section 5.3.

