#### **5.1 Screening Procedures**

**Screening for COVID-19 symptoms and protection measures:** We will follow the standard of care of the Kenya Ministry of Health, KEMRI, and WHO guidelines on the COVID-19 virus. Participants will be informed about practicing good hand hygiene, masking, good respiratory hygiene, and maintaining social distancing. Staff will adhere to social procedures including maintaining a six foot distance and wearing masks. Unvaccinated participants and staff will be screened for COVID-19-related symptoms when they arrive at the clinic using a checklist to check for risk of COVID-19 exposure based on symptoms or contacts. Any person that comes to the clinic with symptoms consistent with COVID-19 that include 1 or more of fever, cough (dry or productive), dyspnea, or myalgias will be isolated. Participants will be educated about the Ministry of Health specified measures for seeking healthcare during this time. Referral

mechanisms to local public health facilities are in place. Finally, the clinical site will maintain a register of all visitors and participants who enter the study site, to support usual care contact tracing efforts where necessary.

At the screening visit a qualified study clinician will perform a history and physical exam for each participant. A complete medication history will be obtained including all drug allergies, immunization history, prescription, over the counter, and herbal treatments. Vital signs will include height, weight, blood pressure, pulse, respiratory rate and temperature. The following procedures will be conducted:

- Informed consent
- Safety Labs: Complete blood count (CBC, specifically hematocrit and hemoglobin), HBV surface antigen, serum creatinine)
- HIV antibody (rapid test or blood)
- Urine pregnancy test
- Medical, medication, vaccine history
- Physical exam

A screening test(s) may be repeated within the 30-day screening window. A participant who is unable to schedule a study entry visit within the 30-day screening window must be re-screened prior to entry into the study. Participants who have not been immunized for HBV will be offered vaccination, as per standard of care. An HBV Antibody test may be ordered for participants who are unsure of their vaccination history.

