#### **Clinic visit 1: Study entry visit (must be within 30 days after screening visit)**

- Medical, sexual, contraception, antenatal and vaccine history review
- Study blood work: WB, DBS, PBMC, plasma, (pre-drug for endogenous molecules such as nucleosides)
- Urine pregnancy test (urine  $\beta$  HCG)
- Study urine: (baseline endogenous molecules such as nucleosides)
- STI tests (CT, GC, syphilis, HSV-2)
- Blood work: hDNA for those who consent to drug transport gene testing
- Vaginal swab
- Dispense back up PrEP medication: subject home supply
- Dispense study dosing calendar
- DOT: Witness first PrEP dose

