##### ***Blood***

A blood sample will be obtained at protocol specified visits to process plasma, whole blood, DBS, and PBMCs. On a given study day blood collection, up to 21mL of blood for study bloodwork will be drawn with no planned timing relationship with dosing. The blood will be collected from an arm vein by trained clinic staff according to study site policies and procedures.

The schedule of protocol visits and procedures are outlined in Table 2.

Table 2: Schedule of protocol visit schedule and procedures.

Timeline (weeks)	Screening	Entry	DOT PrEP Period (weeks)											Post DOT Period	
			W1		W2	W3	W4	W5	W6	W7	W8	W9	W10	W11	W12-18
			Day 4	Day 7											
Clinic Visits #		1	2	3	4	5	6	7	8	9	10	11	12	13	14
Procedure															
Informed consent	x														
Medical, sexual, contraception, antenatal history review, vaccine history	x	x	x	x	x	x	x	x	x	x	x	x	x		
Physical exam a	x														
Dispense back up PrEP medication e		x													
Issue medical calendar		x													
AE assessment		x	x	x	x	x	x	x	x	x	x	x	x		
Safety Labs a,c	x	[x]											x		
Urine βHCG a	x	[x]						x				x			
HBS Ag	x														
HIV-1 rapid test a	x	[x]						x			x				
Hair collection							x			x		x			x
hDNA	x		x												
Study Bloodwork d (WB, plasma, DBS, PBMC)*PBMC is collected bi-weekly		x	x	x	x	x	x	x	x	x	x	x	x	x	x
Vaginal tissue f			x	x			x					x			
Vaginal swab		x	x	x			x				x		x		
DBS by fingerstick			x	x			x				x		x		
Study Urine d		x	x	x	x	x	x	x	x	x	x	x	x	x	x
Concomitant Medication Review	x	x	x	x	x	x	x	x	x	x	x	x	x		
STI testing (CT,GC, syphilis, HSV-2)		x											x		
DOT b		x	x	x	x	x	x	x	x	x	x	x	x		

[x] Indicated if screening occurred more 30 days before planned enrollment. The screen and entry visits must be ≤ 30 days apart.

a. Safety labs or vitals can be performed as needed at any time

b. DOT performed if applicable per randomization schedule

c. Protocol-specified safety labs include: CBC, HbAg, Creatinine clearance, in addition to monthly HIV testing and urine pregnancy tests.

d. Study Bloodwork: WB, DBS, PBMC, plasma and all available blood cell types; Study Urine: endogenous molecules such as nucleosides.

\*PBMC is collected bi-weekly (baseline, week 2, 4, 6, 8, 10)

e. Study medications will be dispensed as described

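### The schedule does not deliver the promised four-weekly HIV testing around the first dose: the last test may be 30 days old at entry, and the next is at week 4

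*Combined protocol and SAP*

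**What the plan says.** **The promise.** Section 8.4, on non-daily dosing, states "All participants in this study will have HIV test at baseline and then every 4 weeks". Section 8.5 says the same under non-daily dosing and under other study procedures. Under TAF-FTC risks it also lists HIV among the tests done at baseline.

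**The safety-lab rule.** Section 4.7 says "Safety related laboratory testing will be performed at study entry and at week 8", and of the labs, "These include HIV rapid testing, complete blood count, HBV surface antigen, serum creatinine, and urine pregnancy test". Between these two statements it adds "If enrollment occurs more 30 days after screening, entry safety labs will be repeated".

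**Order of testing and dosing.** Section 4.8 requires testing at the monthly visits and then says "HIV rapid testing and specimen collection will be completed prior to administration of study medication".

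**The entry visit.** The clinic visit 1 list in Section 5.2.2 includes a urine pregnancy test and STI tests and ends with "DOT: Witness first PrEP dose". It names no HIV test. The lists for weeks 4, 8 and 10 each name one; those for visits 13 and 14 do not.

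**Table 2.** The HIV test at entry is bracketed, and the footnote to the bracket reads "x] Indicated if screening occurred more 30 days before planned enrollment. The screen and entry visits must be ≤ 30 days apart" (its opening bracket is cut off here). Section 5.1 says that a participant who misses the 30-day limit "must be re-screened prior to entry into the study", and Section 5.2 has the same rule.

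**The concern.** The risk sections describe a safeguard for every participant. The operational text that a site works from does not clearly schedule it at the visit where drug is first given. Two things are at stake.

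- **Safety.** Section 4.8 explains that frequent testing allows drug to be stopped promptly, so that resistant virus is less likely to emerge. A woman infected between screening and entry would start drug and could take it for four weeks before her next scheduled test.
- **Classification.** Primary outcome 1 in Section 7.3.1 counts emergent HIV infection. No rule says whether an infection acquired before entry but first detected at week 4 is prevalent or emergent. The label could also affect replacement: under Section 3.8 seroconversions are not replaced, while women who permanently stop dosing are.

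**Working it through.** The plan gives no figure on this point to reproduce. The check compares the texts and then does simple arithmetic. The visit lists in Section 5.2.2 are used for test dates, because column positions in Table 2 may not have survived conversion.

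**1. Can the conditional entry test ever apply?** Let g be the days from screening to entry. Section 4.7 and the Table 2 footnote require the test if g > 30. The same footnote and Sections 5.1 and 5.2 require g ≤ 30. No value of g meets both. Beyond 30 days the participant is re-screened, with a new screening test and a new 30-day limit.

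**2. Is the omission at visit 1 just a loose list?** Partly possible: the visit 1 list also omits the adverse event assessment that Table 2 marks at entry. But the pregnancy test carries the same bracket in Table 2 and is listed at visit 1 without condition, and the lists for weeks 4, 8 and 10 do name the HIV test. A site working from the list would test for pregnancy and STIs at entry, but not for HIV.

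**3. Gap between scheduled tests around the first dose.** Gap = g + 28 days, with the next test at week 4.
- g = 0: 28 days
- g = 15: 15 + 28 = 43 days
- g = 30: 30 + 28 = 58 days
- g = 30, with week 4 at the end of the 10-day window in Section 5.2.2 (assuming the window covers the HIV test): 58 + 10 = 68 days

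With a test at entry the longest gap is 28 days, or 38 with the window.

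**4. Ambiguity of a first positive at week 4.** Assume constant incidence and that every infection since screening is found at week 4. The share that predates entry is g/(g + 28): 15/43 = 35% at 15 days and 30/58 = 52% at 30 days.

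**5. Expected infections between screening and entry.** The documents give no incidence for this low-risk group, so 0.5% and 1% per year are assumptions. As an upper illustration, Section 1.1.1 cites nearly 4% in sexually active women in a contraceptive trial, read here as per year. Expected number = 54 × g/365.25 × rate, and P(at least one) = 1 − exp(−expected).
- g = 15: 54 × 15/365.25 = 2.218 person-years, giving 0.011 and 0.022 at 0.5% and 1%; 0.089 at 4%
- g = 30: 54 × 30/365.25 = 4.435 person-years, giving 0.022 and 0.044 at 0.5% and 1%; 0.177 at 4%
- P(at least one) at g = 30: 2.2%, 4.3% and 16%

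The g = 30 row assumes that every woman waits the full interval.

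**The case against.** The strongest reply is that baseline means screening. Section 6.8.4 glosses the baseline creatinine clearance as the screening value. Section 8.5 puts hepatitis B testing at baseline and uses the results to decide who is enrolled, and that test is in the screening list but not in the visit 1 list. Section 4.7 can then be read to mean that screening labs serve as entry labs while they are valid. The sentence on order in Section 4.8 follows one about monthly visits, so it need not govern entry. There are mitigations too: suspected acute infection is an exclusion (Section 3.2), history is reviewed at entry, Table 2 allows safety labs as needed at any time, and women at substantial HIV risk are excluded.

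Much of this stands. A reader might infer that the sections flatly contradict each other; the documents do not establish that, because the screening reading is tenable. It is not the only reading, since Table 2's PBMC footnote uses baseline for the collection before week 2, which is the entry visit. A reader might also infer that women could be dosed with no HIV test at all. That is wrong: every participant must test negative to be eligible, and must enter within 30 days of screening.

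The screening reading still does not rescue the promise. A test up to 30 days before entry followed by one at week 4 is not testing every 4 weeks.

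**Conclusion.** The point holds and is minor. On either reading of baseline, the schedule allows up to 58 days between tests around the first dose (68 with the visit window) against a promised four weeks. It also leaves an infection acquired before entry exposed to drug and indistinguishable from an emergent one. Under the assumed 0.5 to 1% per year, the chance of even one such infection is at most about 4%. The HIV component of primary outcome 1 is a rare-event count, and the pharmacokinetic conclusions do not depend on it. The case for change is participant safety and a clean definition, not bias in the main results.

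A reader might go further and infer that the outcome has no ascertainment window. The documents do not support that. Section 7.3.1 names the study period, Section 5.2 gives 18 weeks of follow-up, Section 6.3 starts adverse event capture after randomisation, and Section 6.9 runs serious event reporting from enrolment to the end of follow-up. What is missing is a definition of the term for this outcome, given that no HIV test is scheduled after week 10. That is a clarification only. Testing during the drug-free visits would be a preference, since the stated purpose of testing is to stop drug promptly.

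**What to change.** Make the HIV rapid test at entry unconditional and complete it before the first dose.

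- Add it to the clinic visit 1 list.
- Remove the brackets at entry in the HIV row of Table 2.
- Remove HIV testing from the conditional repeat in Section 4.7.
- State that a positive entry test is prevalent infection, prevents dosing, and does not count towards emergent infection in primary outcome 1.

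The test narrows the ambiguity but may not end it: Section 3.2 already adds a clinical exclusion for suspected acute infection alongside the rapid test, and that should stay.

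The cost is wording plus 54 rapid tests at a visit that already draws blood. If the replacement allowance in Section 3.8 is used in full, 0.20 × 54 = 10.8, so at most 10 more women and 64 tests.

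Separately, one sentence in Section 7.3.1 should define the study period for emergent infection and say that scheduled HIV testing ends at week 10. That costs no tests.
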